13.4 Quality Control and Quality Assurance

Recordati maintains a robust Quality Management System (QMS) that includes all activities involved in quality assurance and quality control, to ensure compliance with written Standard Operating Procedures as well as applicable global/local GCP regulations and ICH Guidelines.

Audits of investigator sites, vendors, and CRO systems are performed by auditors, independent from those involved in conducting, monitoring or performing quality control of the clinical trial. The clinical audit process uses a knowledge/risk based approach.

Audits are conducted to assess GCP compliance with global and local regulatory requirements, protocols and internal SOPs, and are performed according to written Recordati processes.

Recordati will ensure that the CRO has in place its own Quality Management System to ensure compliance with written Standard Operating Procedures as well as applicable global/local GCP regulations and ICH Guidelines.

14 Protocol adherence

This protocol defines the study objectives, the study procedures and the data to be collected on study participants. Additional assessments required to ensure safety of subjects should be administered as deemed necessary on a case by case basis. Under no circumstances including incidental collection is an investigator allowed to collect additional data or conduct any additional procedures for any purpose involving any investigational drugs under the protocol, other than the purpose of the study. If despite this interdiction prohibition, data, information, observation would be incidentally collected, the investigator shall immediately disclose it to

Recordati and not use it for any purpose other than the study, except for the appropriate monitoring on study participants.

Investigators ascertain they will apply due diligence to avoid protocol deviations. If an investigator feels a protocol deviation would improve the conduct of the study this must be considered a protocol amendment, and unless such an amendment is agreed upon by Recordati and approved by the IRB/IEC and health authorities, where required, it cannot be implemented.

16.1 Appendix 1: List of drugs to be used with caution with LCI699

Osilodrostat should be used with caution when co-administered with CYP1A2 and CYP2C19 substrates with a narrow therapeutic index such as theophylline, tizanidine and mephénytoïn.

Please refer to Section 5.1.5 of the current IB for further information”.

16.2 Appendix 2: Medications with a “Known risk to cause TdP” and with a “Possible risk to cause TdP”

The following e-link provides a list of medications with a “known risk to cause TdP” and with a “possible risk to cause TdP”. These medications are prohibited to be used concomitantly with LCI699: crediblemeds.org.

Investigators are advised to utilize this website when considering the addition of a new concomitant medication, as the lists are periodically updated. If necessary, a discussion can be held with the Recordati Medical Monitor when considering the use of medications with a “known risk to cause TdP” and “possible risk to cause TdP”.

## Revision History

Date	Version	Summary of Changes
8 May 2018	1.0	First Version
13 January 2021	1.1	Change of sponsor – reformatting according with SOP 06BM13R02
16 July 2021	2.0	Implementation of protocol amendment 01 Introduction of interim analyses for safety
14 April 2023	3.0	Implementation of protocol amendment 02 Identification of the data from parent studies to complete baseline visit (W1D1) Deletion of output for section 10, 11 and 12
26 May 2023	3.1 (not issued)	Introduction calculation of CTCAE grading for lab parameters
26 June 2023	3.2	Update based on specific issues identified during interim analyses

Study Code: CLCI699C2X01B

## 1 LIST OF ABBREVIATIONS

AE	Adverse Event
ATC	Anatomical Therapeutic Classification
AUC	Area Under the Curve
bid	bis in diem/twice a day
CSR	Clinical Study Report
CTC	Common Toxicity Criteria
CTCAE	Common Terminology Criteria for Adverse Events
DMC	Data Monitoring Committee
FAS	Full Analysis Set
eCRF	Electronic Case Report Form
MedDRA	Medical Dictionary for Drug Regulatory Affairs
NCI	National Cancer Institute
OS	Overall Survival
PFS	Progression-Free Survival
PK	Pharmacokinetics
PPS	Per-Protocol Set
PRO	Patient-reported Outcomes
QoL	Quality of Life
RAP	Report and Analysis Process
RECIST	Response Evaluation Criteria in Solid Tumors
SAP	Statistical Analysis Plan
SOC	System Organ Class
TFLs	Tables, Figures, Listings
WHO	World Health Organization

## 2 INTRODUCTION

This statistical analysis plan (SAP) describes all planned analyses for the clinical study report (CSR) of study CLCI699C2X01B, an open label multi-center roll over study to assess long term safety in patients with endogenous Cushing's syndrome who have completed a prior Novartis -sponsored osilodrostat (LCI699) study and are judged by the investigator to benefit from the continued treatment.

### 2.1 CLINICAL OBJECTIVES

The purpose of the study is to evaluate the long-term safety.

### 2.2 STATISTICAL DESIGN / MODEL

This is a multi-center, open label phase IIb study to evaluate the long-term safety of osilodrostat in subjects receiving osilodrostat from Global Novartis-sponsored studies which has fulfilled its requirement for the primary objective, and who are judged by the parent study investigator as benefiting from continued treatment with osilodrostat.

[figure not shown]
---

Study Code: CLCI699C2X01B

There will be no screening period for this study. Eligible subjects can start their treatment with osilodrostat as soon as they are enrolled in the study. The first study visit will be scheduled at the time of the last study visit for the parent study. Subjects must return to the study center at least on a quarterly basis (every 12 weeks  $\pm$  2 weeks) for safety and clinical benefit assessments, and resupply of study medication. Drug dispensing and administration information and adverse events will be collected. The subject may return to the clinic at any given time as per standard of care or treating physician recommendation. All adverse events and serious adverse events, including pregnancy, will be collected throughout the study.

At every quarterly visit (every 12 weeks  $\pm$  2 weeks), the Investigator is required to confirm that the subject continues to have clinical benefit and may continue receiving study treatment.

Figure 2-1 Study Design

### 2.3 INTERIM ANALYSES

In February 2021 the Pharmacovigilance Risk Assessment Committee (PRAC) requested the study sponsor to provide interim results of this roll-over study within the upcoming Periodic Safety Update Reports (PSURs). Therefore, regular interim analyses have been performed during the course of the study which will be aligned with the submission dates for the PSUR.

The final analysis will occur when all patients complete the study.

For the interim analyses, the following tables/listings have been provided (tables marked with "\*" will be prepared only in case of request from the PRAC):

#### Tables

- Patient disposition (FAS)
- Demographics and baseline characteristics (FAS)
- Disease history (FAS)
- Duration of exposure to study drug during the overall study period excluding the parent study (Safety Set)
- Dose summary during the overall study period excluding the parent study (Safety Set)

---

Study Code: CLCI699C2X01B

- Dose summary during the overall study period including the parent study (Safety Set) \*
- Overview of adverse events (Safety Set)
- Adverse events, regardless of study drug relationship, by system organ class (Safety Set)
- Adverse events, regardless of study drug relationship, in at least 10% patients (All Patients all grades) by preferred term (Safety Set)
- Adverse events, suspected to be study drug related, in at least 5% patients (All Patients all grades) by preferred term (Safety Set)
- Serious adverse events, regardless of study drug relationship, by preferred term (Safety Set)
- Serious adverse events, suspected to be study drug related, by preferred term (Safety Set)
- Adverse events of special interest, regardless of study drug relationship - Adrenal hormone precursor accumulation-related AEs (Safety Set)
- Adverse events of special interest, regardless of study drug relationship - Hypocortisolism-related AEs (Safety Set)
- Adverse events of special interest, regardless of study drug relationship - Arrhythmogenic potential AEs (Safety Set)
- Adverse events of special interest, regardless of study drug relationship - Pituitary tumour enlargement-related AEs (Safety Set)
- Adverse events of special interest, regardless of study drug relationship - QT prolongation AEs (Safety Set)

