1.1 Background

1.1.1 Epidemiology and pathogenesis of Cushing's syndrome

Cushing's syndrome (CS) is a rare disorder with a reported incidence of 0.7–2.4 per million population per year. In European countries and in the US, the prevalence rates have been reported to range from 19 to 79 cases per million inhabitants, with the highest prevalence (79 cases per million) reported from New Zealand. In a survey conducted in Japan by the Ministry of Health, Labour and Welfare in 1997, the prevalence of CS has been reported to be approximately 1250 cases.

CS is characterized by a chronic excess of cortisol secretion, which results in numerous clinical features that are associated with a higher mortality compared with the general population, if not appropriately treated ([Pivonello et al, 2008](#)).

CS can be either exogenous or endogenous. The most common cause of exogenous CS is iatrogenic due to the external administration of excessive doses of glucocorticoids.

Endogenous CS is classified as either adrenocorticotrophic hormone (ACTH)-dependent or ACTH-independent. ACTH-dependent CS accounts for 80%–85% of cases. Of these, 75%–80% are due to ACTH production from a pituitary adenoma (Cushing's disease [CD]), 15%–20% are due to ACTH production from non-pituitary tumors (ectopic ACTH syndrome) and <1% are caused by corticotrophin-releasing hormone (CRH)-producing tumors.

ACTH-independent CS accounts for 15%–20% of endogenous CS in adults; 90% are unilateral adrenal tumors. Of these, adenomas are the cause in ~80% of the cases, while the others are adrenocortical carcinoma.

Cushing's disease (CD) is the most common cause of CS (70% of cases) in Western countries, while it makes up a smaller proportion of the CS population in Japan (35.8%). It is caused by excessive secretion of cortisol from the adrenal glands as a consequence of excessive ACTH secretion from a pituitary tumor, generally an adenoma (90%), whereas a carcinoma is a very rare cause of the disease (less than 10%). It affects adults aged 20–50 years-old more commonly with a marked female preponderance ([Pivonello et al 2008](#); [Newell-Price et al 2006](#)).

Endogenous CS is characterized by chronic hypercortisolism, which results in a variety of metabolic abnormalities and co-morbidities that collectively lead to an overall 4-fold higher mortality rate than age- and gender-matched subjects in the general population ([Arnaldi et al, 2003](#)).

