In Part II, 17 out of 19 patients completed 22 weeks of treatment and 15 had normal cortisol levels at week 22 (79%). During treatment with osilodrostat, the mean cortisol levels decreased quickly and stabilized to a normal level (11 to 138 nmol/24h) at Week 4. After Week 4, normal mean cortisol levels were observed through the study up to Week 22. All patients attained UFC normalization at least once during the study, and no patient “escaped” UFC control. The study is ongoing.

- Two phase III multi-center studies are ongoing:
 - a. C2301: this is a double-blind, randomized, withdrawal study following a 24 week, single-arm, open-label, dose titration and treatment period to evaluate the safety and efficacy of osilodrostat in the treatment of patients with CD. Primary endpoint: proportion of randomized patients in each treatment group with mUFC \leq ULN at week 34 who neither discontinued nor had dose increase above the week 24. This study has enrolled 137 subjects with CD.
 - b. C2302: this is a randomized, double-blind, placebo-controlled 48-week study with an initial 12 week placebo-controlled period to evaluate the safety and efficacy of osilodrostat in patients with CD. Primary endpoint: proportion of randomized patients with a complete response at Week 12. The study plans to enroll 69 subjects with CD.
- One phase II multi-center study is ongoing in Japan:
 - a. C1201: this is an open label, dose titration, multi-center study to assess the safety, tolerability and efficacy of osilodrostat in patients with all types of endogenous CS, except CD.

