5.1 Inclusion criteria

Patients eligible for inclusion in this study must meet **all** of the following criteria:

1. Patient is currently participating in a Global Novartis-sponsored study receiving osilodrostat for any type of endogenous CS and has fulfilled all their requirements in the parent study.
2. Patient is currently benefiting from treatment with osilodrostat, as determined by the Investigator.
3. Patient has demonstrated compliance, as assessed by the Investigator, with the parent study protocol requirements.
4. Willingness and ability to comply with scheduled visits and treatment plans.
5. Written informed consent obtained prior to enrolling into the roll-over study before evaluating the applicability of the subject's participating in the study.
 - If consent cannot be expressed in writing, it must be formally documented and witnessed, ideally via an independent trusted witness.

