## 5.3 DATA FROM PARENT STUDIES

Data referring to the disease history, as well as the height, were not collected in the study EDC but remained in the databases of the parent studies where the patients are coming from.

In addition, the data from the end of the treatment (or last visit) in the parent studies, will be extracted by the parent studies databases and transferred by the sponsor to the CRO. The date of the EOT visit from the parent study will be matched with the date of the baseline (W1D1) to guarantee the proper correspondence. The cases with a discrepancy exceeding one week between the two dates will be evaluated case by case.

For disease history they are the following ones:

- Time (months) to first study osilodrostat dose since diagnosis
- Classification at time of diagnosis
- Cushing's Disease Status
- Any previous surgery
- Any previous, non-LCI, treatments for Cushing's disease
- Any previous pituitary irradiation
- Baseline mean UFC.

---

Study Code: CLCI699C2X01B

---

For W1D1 visit the data to be transferred will regard the following topics:

- Vital signs (domain VS)
- ECG (domain EG)
- MRI (domains PR, FA)
- Laboratory (domain LB)

The data will be extracted as SAS datasets as close as possible to the domain structures reported in attachment 8.2.

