### 6.2 DEFINITION OF POPULATIONS FOR ANALYSIS

#### 6.2.1 Full Analysis Set

6.2.2 For this study, the definition of FAS is the same as the Safety Set and in the tables the Safety Set will be indicated. Safety Set

The Safety Set includes all patients who received at least one dose of study medication (Osilodrostat) after enrolling into the roll-over protocol.

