III nerve paresis	10054202	AESI Pituitary tumor enlargement-related AEs
IV nerve disorder	10065836	AESI Pituitary tumor enlargement-related AEs
IV nerve injury	10023108	AESI Pituitary tumor enlargement-related AEs
IV nerve paralysis	10023110	AESI Pituitary tumor enlargement-related AEs
IV nerve paresis	10054201	AESI Pituitary tumor enlargement-related AEs
Microvascular cranial nerve palsy	10079491	AESI Pituitary tumor enlargement-related AEs
Neoplasm progression	10061309	AESI Pituitary tumor enlargement-related AEs
Neoplasm recurrence	10061864	AESI Pituitary tumor enlargement-related AEs
Optic nerve compression	10076302	AESI Pituitary tumor enlargement-related AEs
Pituitary apoplexy	10056447	AESI Pituitary tumor enlargement-related AEs
Pituitary enlargement	10048675	AESI Pituitary tumor enlargement-related AEs
Pituitary haemorrhage	10049760	AESI Pituitary tumor enlargement-related AEs
Pituitary infarction	10035092	AESI Pituitary tumor enlargement-related AEs
Pituitary tumour	10035104	AESI Pituitary tumor enlargement-related AEs
Pituitary tumour benign	10061538	AESI Pituitary tumor enlargement-related AEs
Pituitary tumour recurrent	10057316	AESI Pituitary tumor enlargement-related AEs
Tumour compression	10068268	AESI Pituitary tumor enlargement-related AEs
Tumour invasion	10064390	AESI Pituitary tumor enlargement-related AEs
VI nerve disorder	10053646	AESI Pituitary tumor enlargement-related AEs
VI nerve injury	10047639	AESI Pituitary tumor enlargement-related AEs
VI nerve paralysis	10047641	AESI Pituitary tumor enlargement-related AEs
VI nerve paresis	10071044	AESI Pituitary tumor enlargement-related AEs
Visual field defect	10047555	AESI Pituitary tumor enlargement-related AEs
Electrocardiogram QT interval abnormal	10063748	AESI QT prolongation AEs
Electrocardiogram QT prolonged	10014387	AESI QT prolongation AEs
Long QT syndrome	10024803	AESI QT prolongation AEs

Study Code: CLCI699C2X01B

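### The final pituitary-tumour AESI summary has no column for Cushing's disease patients alone and no rule for attributing site-free tumour terms

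*SAP*

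**What the plan says.** **Population of the table.** SAP 2.3 lists the interim AESI table as "Pituitary tumour enlargement-related AEs (Safety Set". SAP 7.4.1 lists and summarises AESIs for the report on the same set, taking the categories from Attachment 8.1. The set is defined without regard to aetiology: "The Safety Set includes all patients who received at least one dose of study medication (Osilodrostat) after enrolling into the roll-over protocol". SAP 6.2.3 names no subgroup of interest. Breakdown by indication and formulation is promised for the disposition, consent and eligibility listings (SAP 4.2.1) and for protocol deviations (SAP 6.1), but not for AESIs.

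**Who may enter.** Inclusion criterion 1 (Protocol 5.1) admits patients "receiving osilodrostat for any type of endogenous CS". Protocol 1.2.1.2.1 describes one ongoing osilodrostat study, C1201 in Japan, in "patients with all types of endogenous CS, except CD".

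**What the category contains.** Most terms under the pituitary heading in Attachment 8.1 name the pituitary or a cranial-nerve or visual effect. Four are tumour terms with no anatomical site: "Neoplasm progression", Neoplasm recurrence, Tumour compression and Tumour invasion. Neither SAP 7.4.1 nor the attachment says how the site is to be established before such an event is counted.

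**Aetiology data.** SAP 4.2.2 lists the parent study number for each patient. SAP 5.3 transfers "Classification at time of diagnosis" from the parent databases.

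**The concern.** Protocol 4.5 names corticotroph tumour progression as a potential risk of treatment, and two patients in C2201 Part II had pituitary tumour events (Protocol 1.2.1.2.2). A percentage printed under this AESI heading will be read as the frequency of that risk.

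By the protocol's own account of the disease (1.1.1), the pituitary adenoma belongs to Cushing's disease. The other forms arise elsewhere: within ACTH-dependent disease "15%–20% are due to ACTH production from non-pituitary tumors", and ACTH-independent disease is mostly due to adrenal tumours, some of them carcinomas. Two things follow if such patients are in the roll-over:

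- They add to the denominator but cannot contribute a corticotroph event.
- Progression, recurrence, invasion or compression of their own tumour, if coded to a site-free term, is tabulated as pituitary enlargement.

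A reader of the Safety Set figure alone could not tell how much either effect had changed it.

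**Working it through.** The plan offers no figure to reproduce. Sample size is not applicable (Protocol 12.8), no hypothesis is tested (SAP 7.1.2) and no AESI rate is stated. The check is therefore simple proportions, with the unknowns set as assumptions.

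**Inputs**

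- N = 100 treated patients. The documents give 100 enrolled at 8 April 2020 (Protocol, Amendment 02 rationale). This is not stated to be the final number, so it serves only as a scale.
- k = non-CD patients. Not given, so assumed at 5, 10 and 20.
- x = CD patients with a true pituitary event. Not given, so assumed.
- m = non-CD patients with a non-pituitary tumour event coded to a site-free term. Not given, so assumed at 0, 1 and 2.

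**Formulas**

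- Safety Set percentage = (x + m)/N
- Percentage among CD patients = x/(N − k)
- With m = 0, CD percentage = Safety Set percentage ÷ (1 − k/N)
- The two errors cancel when m = xk/(N − k)

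**Denominator effect alone (m = 0), for an assumed observed 10%**

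- 5% non-CD: 10%/0.95 = 10.5%
- 10% non-CD: 10%/0.90 = 11.1%
- 20% non-CD: 10%/0.80 = 12.5%

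**Numerator effect alone.** One misattributed patient adds 1/100 = 1 percentage point.

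**Both together, with x = 5 and N = 100**

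| k | CD only, 5/(100 − k) | Safety Set, m = 0 | m = 1 | m = 2 | Cancelling m |
|---|---|---|---|---|---|
| 5 | 5.26% | 5.00% | 6.00% | 7.00% | 0.26 |
| 10 | 5.56% | 5.00% | 6.00% | 7.00% | 0.56 |
| 20 | 6.25% | 5.00% | 6.00% | 7.00% | 1.25 |

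With 10 non-CD patients, the Safety Set figure is below the CD figure when m = 0 and above it when m = 1. With 20, it is still below at m = 1 and above at m = 2. One or two events therefore decide the sign of the discrepancy. With k = 0 both errors vanish.

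**The case against.** **The non-CD group may be small or empty.** Criterion 1 permits non-CD patients, but no document says that any enrolled. C1201 is described without a sample size, and nothing states that its patients rolled over. The studies with stated sizes are all in CD: 19 patients in C2201 Part II, 137 in C2301 and 69 planned in C2302. This stands, and it is why no size can be claimed.

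**The shift is within the noise.** The exact 95% interval for 10/100 is about 4.9% to 17.6%, so a move to 10.5–12.5% lies well inside it, and no decision threshold depends on the figure. That limits the weight of the point. It does not remove the value of stating who is at risk.

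**Partial safeguards exist.** A dedicated listing of these AEs allows case review, a disease history table is planned, and SAP 2.3 lets outputs be added. Protocol 10.1.1 asks for a diagnosis to be recorded where possible, which makes a site-free code less likely. None of these is a pre-specified summary in CD patients or a rule for attribution.

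**The site-free terms have a proper use.** In a CD patient they catch pituitary growth reported without a site. This stands: the gap is the missing rule, not the presence of the terms.

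**Stronger readings that the documents do not support**

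- *The table understates the risk.* The numerator error works the other way, so the net direction is open.
- *The Safety Set is the wrong population.* The objective is long-term safety in roll-over patients, and Protocol 12.5.1.1 assigns all safety analyses to this set. The overall figure is valid for that question. The CD figure supplements it.
- *The MRI summaries share the fault.* SAP 7.4.5 summarises measured volume or longest dimension and its change, not a percentage of the Safety Set, so the denominator argument does not carry over.
- *The interim tables need correcting.* SAP 2.3 says that they have already been provided. What remains open is the final summary and any further PSUR output.

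**Conclusion.** The point holds as a gap in specification. The final AESI summary gives pituitary tumour enlargement only over all treated patients of any aetiology, and four tumour terms without a site count towards it with no attribution rule.

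Its size is not established. The shifts of 0.5 to 2.5 percentage points on an observed 10% rest on assumed non-CD shares of 5% to 20%. The 1 point per misattributed event rests on about 100 patients. Both effects are nil if no non-CD patient was treated. The case for acting is that the change is cheap and gives the percentage among the patients to whom the named risk applies.

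**What to change.** For the final analysis and any further PSUR output:

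1. Keep the Safety Set table of pituitary tumour enlargement-related AEs.
2. Add CD and non-CD columns to it, each with its own denominator. Take aetiology from the parent study number (SAP 4.2.2): the protocol describes C1201 as excluding CD, and C2201, C2301 and C2302 as CD studies. Use the classification at diagnosis (SAP 5.3) as well if it records aetiology. The SAP does not define that item and its neighbours are specific to CD, so check this first.
3. State in SAP 7.4.1 or Attachment 8.1 that the four site-free terms count as pituitary events only where the AE record indicates a pituitary tumour. Give the number of events set aside in a footnote, so that the table can be reconciled with the interim ones. Those events remain in the general AE tables.

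The cost is one extra set of columns, a check of the AE record for any event coded to the four terms, and a slightly smaller denominator in the CD column. If no non-CD patient enrolled, one sentence in the report saying so is enough.
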